5.2.4 Electrocardiogram

At start of run-in and end of treatment, a complete physical examination will be performed by the investigator or qualified designee (see [Flow Chart](#)). Documentation of, and findings from the physical examination, must be part of the source documents available at the site.

Printed paper traces from 12-lead ECGs (I, II, III, aVR, aVL, aVF, V1-V6) will be collected at screening. ECG traces on thermopaper should be copied to normal paper to avoid fading. In the event of any cardiac symptoms (i.e. suspicion of heart rhythm disorders or cardiac ischemia), an additional ECG will be recorded. All ECGs will be evaluated, (signed, dated and commented upon) by the treating physician/investigator and stored locally. Any clinically relevant changes in the ECG will be reported as AEs and followed up and/or treated locally until normal or stable condition. Any ECG abnormalities will be carefully monitored and if necessary the patient will be removed from the trial and medically treated.

5.2.5 Assessment of other safety parameters

All patients will be provided with HBGM equipment and supplies for use at home during the 2-week Run-In Period. Instruction on the proper use of the HBGM will be provided by the study staff. The patient will be asked to record the results of the HBGM test on a HBGM Testing Log that will be included in the patients source document file. Only in the case of linked adverse events or of hypoglycemia, the single HBGM values will be recorded in the CRF. The respective procedure for illiterate patients (if included) is described in the [Appendix 10.1](#). Even though review of the HBGM log is required, electronic review of the

Proprietary confidential information.

[figure not shown]
© 2016 Boehringer Ingelheim International GmbH or one or more of its affiliated companies. All rights reserved.

This document may not - in full or in part - be passed on, reproduced, published or otherwise used without prior written permission.

glucometer is not required. If a patient forgets to return their Log, they should be reminded to record HBGM values on the Log and return it at the next visit.

During Run-In and Follow-up, HBGM testing should be performed once daily in the fasted state and at any time the patient is symptomatic, i.e., experiences signs/symptoms of hyper- or hypoglycemia. If during Run-in, results of a HBGM test reveal blood glucose of >270 mg/dl (>15.0 mmol/L) after an overnight fast the patient should contact the site. Patient should also eat or drink something immediately and contact the site in the event that blood glucose level drops below 54 mg/dl (3.0 mmol/l). The investigator should then decide about start of the randomised period or further patient participation in the trial based on fasted plasma glucose determinations according to the inclusion and exclusion criteria as outlined in [Section 3.3](#).

[figure not shown]
During the randomised treatment period, HBGM testing should be performed once weekly (more frequently if required by local authorities) and at any time the patient is symptomatic, i.e., experiences signs/symptoms of hyper- or hypoglycemia. If during this period, results of a fasting HBGM test reveal blood glucose levels meeting rescue criteria (see [Section 4.2.1](#)), the patient should contact the site and the investigator should follow the instructions given in Section 4.2.1.

Proprietary confidential information.

6. INVESTIGATIONAL PLAN

6.1 VISIT SCHEDULE

All trial visits with the exception of ABPM visits should be routinely scheduled in the morning, at approximately the same time of day (07:00 AM to 11:00 AM). For ABPM visits, patients should arrive at approximately half an hour prior to medication intake to allow additional time for ABPM procedures, so that dosing of medication occurs as close as possible to patient daily dosing time. If a patient mistakenly takes trial medication on the morning of a visit before attending the clinic (excluding visits starting before randomisation) or comes in non-fasted where a fasting condition is required (all visits except screening), the visit should be rescheduled for another day as soon as possible reminding the patient about the expected conditions. The rescheduled visit must take place in a short enough time-frame so that the patient has sufficient trial medication available. Fasting visits should take place at a minimum of 10 hours after the end of the patient's last meal.

Patients who are fasting (e.g. for religious or cultural reasons) should be instructed to perform HBGM tests regularly and to contact the site in case of signs/symptoms or values suggestive hypoglycemia.

All patients are to adhere to the visit schedule as specified in the [Flow Chart](#). If any visit has to be rescheduled, subsequent visits should follow the original visit date schedule. The trial medication packs contain sufficient medication to allow for these time windows.

6.2 DETAILS OF TRIAL PROCEDURES AT SELECTED VISITS

Study procedures to be performed at each visit are listed in the Flow Chart. Additional details regarding visit procedures are provided below. All visits, except Visit 1, must be performed in fasted state (10 hours without food and only water).

6.2.1 Screening and run-in period

Visit 1 (Screening)

- The screening visit is the only visit in this study that does not need to be done fasting.
- No trial procedures should be done unless the patient has consented to taking part in the trial. Patient identification numbers are available in the RDC system. If a patient is re-screened, a new patient identification number should be assigned.
- Once they have consented, the patient is considered to be enrolled in the trial and to have started screening. The patient should be recorded on the enrolment log and registered in the IRT system as a screened patient.
- BP should always be measured before any blood samples are taken. For details regarding the correct method for measuring BP, please see [Appendix 10.3](#).
- Once Visit 1 procedures are complete and laboratory results are received, inclusion/exclusion criteria must be reviewed. If the patient meets inclusion/exclusion criteria, the patient should be contacted to schedule next visit. If the patient does not meet

Proprietary confidential information.

© 2016 Boehringer Ingelheim International GmbH or one or more of its affiliated companies. All rights reserved.

This document may not - in full or in part - be passed on, reproduced, published or otherwise used without prior written permission.

inclusion/exclusion criteria the patient must be recorded in CRFs and registered in the IRT system as a Screen failure.

Visit 2.1 (Run-in period)

- From this visit onwards, patients should be fasting (no food or drinks, water only for at least 10 hours) prior to each visit.
- Inclusion/exclusion criteria must be reviewed at this visit
- BP should always be measured before any blood samples are taken. For details regarding the correct method for measuring BP, please see [Appendix 10.3](#).
- Collection of urine and blood for laboratory testing must be performed prior to administration of study medication.
- Provide patient with diet and exercise counseling. Patients should be given a food log to be completed for three consecutive days prior to Visit 3 as indicated in the [Flow Chart](#).
- Provide HBGM equipment/supplies and instruct patient on the correct use of HBGM.
- Instruct patient to perform a HBGM once daily during the run-in period in the fasted state and at any time the patient is symptomatic, i.e., experiences signs/symptoms of hyper or hypoglycemia. Instruct patient to contact site immediately if blood glucose reaches the limit described in [Section 4.2.1](#).
- Once all visit procedures are conducted, contact the IRT system to obtain run-in medication kit number and dispense the medication to the patient.
- Administer dose of medication.
- Remind the patient to arrive half an hour earlier for the next scheduled visit (Visit 2.2).
- Instruct patients NOT to take study medication on the morning of the next trial visit.

Visit 2.2 (Baseline ABPM visit)

- ABPM should be done during the run-in period within 7 days prior to Visit 3.
- The ABPM device is attached to the patient and proper operation of the device should be ensured.
- Record the time the medication was administered and the time the monitor was prompted to take the Beginning of Test reading.
- Instruct the patient on the proper use of the ABPM device . The monitor should remain on the patient for at least 24 hours. The patient should be instructed to not remove the monitor and schedule a visit for the next day for removal of the monitor if possible. Patient should arrive early again for the visit on the next day.
- The next day when the patient returns to the clinic (within 23:30-24 hours of the beginning of the test), prompt the monitor to take a Conclusion of Test reading. If an invalid reading occurs for the Conclusion of Test reading, continue to trigger a manual reading until a valid reading is registered. The monitor will then be removed and the time of the Conclusion of Test will be recorded.
- Once the data from the session is downloaded, review the QC results to determine if the session was technically successful. Remember to record the 24-hour mean SBP displayed

Proprietary confidential information.

© 2016 Boehringer Ingelheim International GmbH or one or more of its affiliated companies. All rights reserved.

This document may not - in full or in part - be passed on, reproduced, published or otherwise used without prior written permission.

at the bottom of the QC results. The 24-hour mean SBP at this visit together with a successful session determines eligibility for randomization.

- If the first ABPM attempt was unsuccessful (failed QC and/or the mean ABPM SBP is outside the required range), repeat it within 2 days. Patients having two unsuccessful baseline ABPM sessions should not be randomised and must be discontinued.
- If ABPM was successful, the patient is eligible for randomization and procedures for Visit 3 can be conducted on the same day after the ABPM device is removed and trough seated blood pressure measurement is taken. If conducted on the same day, procedures for Visit 3 should be done prior to administering study medication.
- Allow the patient to rest for at least 15 minutes after the monitor is removed. Then take a seated blood pressure measurement. Record the time of this measurement. This should be done prior to administering study medication.
- For further instructions for ABPM measurements, please see [Section 5.1.2](#).
- Instruct patients NOT to take study medication on the morning of the next trial visit.

Patients who fail the run-in period following Visit 2 procedures should be registered as a screen failure in the IRT system.

6.2.2 Treatment period

The treatment period is from Visit 3 to Visit 7.2. Patients will be dispensed medication at Visits 3, 4, and 5.2. Patients will receive a new kit number through the IRT system on each occasion. Assessments should be performed as mentioned in the [Flow Chart](#) and the respective protocol sections.

Throughout the treatment period, BP should always be measured before any blood samples are taken. For details regarding the correct method for measuring BP, please see [Appendix 10.3](#).

Visit 3 (Randomisation visit)

- Inclusion/exclusion criteria must be reviewed prior to randomization
- BP measurement and orthostatic blood pressure test should always be done before taking any blood sample.
- Collection of urine and blood for laboratory testing must be performed prior to administration of study medication.
- Collect returned run-in medication.
- Collect blood sample for PG evaluation after obtaining separate informed consent. PG sample should be collected for randomised patients only.
- Patients should be reminded about the importance of following the agreed diet and exercise plan. Patients should be given a food log to be completed for three consecutive days prior to Visit 4 as indicated in the Flow Chart.
- Provide HBGM equipment/supplies and instruct patient on the correct use of HBGM.

Proprietary confidential information.

- Instruct patient to perform a HBGM once weekly during the treatment period (more frequently if required by local authorities) in the fasted state and at any time the patient is symptomatic, i.e., experiences signs/symptoms of hyper or hypoglycemia. Instruct patient to contact site immediately if blood glucose reaches the limit described in [Section 4.2.1.](#)
- Once all visit procedures are conducted, contact the IRT system to randomise the patient and obtain medication kit numbers and dispense the medication to the patient.
- Administration first dose of study medication.
- Instruct patients NOT to take study medication on the morning of the next trial visit.

Visit 4

- BP should always be measured before taking any blood samples.
- Collection of urine and blood for laboratory testing must be performed prior to administration of study medication at each visit.
- Collect returned medication.
- New medication kit must be dispensed according to the [Flow Chart](#), and the IRT system must be contacted to obtain medication kit numbers to be dispensed.
- Patients should be reminded about the importance of following the agreed diet and exercise plan. Patients should be given a food log to be completed for three consecutive days prior to Visit 5.2 as indicated in the Flow Chart.
- Provide HBGM equipment/supplies and instruct patient on the correct use of HBGM.
- Instruct patient to perform a HBGM once weekly during the treatment period (more frequently if required by local authorities) in the fasted state and at any time the patient is symptomatic, i.e., experiences signs/symptoms of hyper or hypoglycemia. Instruct patient to contact site immediately if blood glucose reaches the limit described in [Section 4.2.1.](#)
- Once all visit procedures are conducted, contact the IRT system to obtain medication kit numbers (Dose escalation kit) and dispense the medication to the patient. Administer dose of study medication.
- Remind the patient to arrive half an hour earlier for the next scheduled visit (Visit 5.1).
- Instruct patients NOT to take study medication on the morning of the next trial visit.

Visit 5.1 (Week 12 ABPM visit)

- ABPM should be done within 7 to 2 days prior to Visit 5.2.
- Attach ABPM device to the patient and initiate the test readings to ensure the monitor is operating properly.
- Administer study medication on the morning of the study visit after the test readings have confirmed that the device is operating properly. Record the time the medication was administered and the time the monitor was prompted to take the Beginning of Test reading.
- Instruct the patient on the proper use of the monitor. The ABPM device should remain on the patient for at least 24 hours. The patient should be instructed not to remove the

Proprietary confidential information.

© 2016 Boehringer Ingelheim International GmbH or one or more of its affiliated companies. All rights reserved.

This document may not - in full or in part - be passed on, reproduced, published or otherwise used without prior written permission.

monitor and schedule a visit for the next day for removal of the monitor. Patient should arrive early again for the visit on the next day.

- The next day when the patient returns to the clinic (within 23:30-24 hours of the beginning of the test), prompt the monitor to take a Conclusion of Test reading. If an invalid reading occurs for the Conclusion of Test reading, continue to trigger a manual reading until a valid reading is registered. The monitor will then be removed and the time of the Conclusion of Test will be recorded.
- If ABPM was successful, procedures for Visit 5.2 can be conducted on the same day after the ABPM device is removed and trough seated blood pressure measurement is taken. If conducted on the same day, procedures for Visit 5.2 should be done prior to administering study medication.
- If the first ABPM attempt was unsuccessful (failed QC), a repeat reading should be taken within 2 days. Patient having two technically unsuccessful ABPM sessions may continue with Visit 5.2. Procedures for Visit 5.2 can be conducted on the same day after the ABPM device is removed and trough seated blood pressure measurement is taken.
- Allow the patient to rest for at least 15 minutes after the monitor is removed. Then take a seated blood pressure measurement. Record the time of this measurement. This should be done prior to administering study medication.
- Administer dose of study medication.
- For further instructions for ABPM measurements, please see [Section 5.1.2](#).
- Instruct patients NOT to take study medication on the morning of the next trial visit.

Visit 5.2

- BP and orthostatic blood pressure test should always be done before taking any blood samples.
- Collection of urine and blood for laboratory testing must be performed prior to administration of study medication at each visit.
- PK trough sample should be collected within 30 minutes prior to intake of study medication.
- Collect returned medication.
- New medication kit must be dispensed according to the [Flow Chart](#), and the IRT system must be contacted to obtain medication kit numbers to be dispensed.
- Patients should be reminded about the importance of following the agreed diet and exercise plan. Patients should be given a food log to be completed for three consecutive days prior to Visit 7.2 as indicated in the Flow Chart.
- Provide HBGM equipment/supplies and instruct patient on the correct use of HBGM.
- Instruct patient to perform a HBGM once weekly (more frequently if required by local authorities) in the fasted state and at any time the patient is symptomatic, i.e., experiences signs/symptoms of hyper or hypoglycemia. Instruct patient to contact site immediately if blood glucose reaches the limit described in [Section 4.2.1](#).
- Once all visit procedures are conducted, contact the IRT system to obtain medication kit numbers (Dose escalation kit) and dispense the medication to the patient. Administer dose of study medication.

Proprietary confidential information.

© 2016 Boehringer Ingelheim International GmbH or one or more of its affiliated companies. All rights reserved.

This document may not - in full or in part - be passed on, reproduced, published or otherwise used without prior written permission.

- Instruct patients NOT to take study medication on the morning of the next trial visit.

Visit 6 (Phone visit)

- Remind the patient to arrive half an hour earlier for the next scheduled visit (Visit 7.1).
- Instruct patients NOT to take study medication on the morning of the next trial visit.

Visit 7.1

- ABPM should be done within 7 to 2 days prior to visit 7.2.
- Attach ABPM device to the patient and initiate the test readings to ensure the device is operating properly.
- Administer study medication on the morning of the study visit after the test readings have confirmed that the device is operating properly. Record the time the medication was administered and the time the monitor was prompted to take the Beginning of Test reading.
- The ABPM device should remain on the patient for at least 24 hours.
- Instruct the patient on the proper use of the monitor. The patient should be instructed not to remove the monitor and schedule a visit for the next day for its removal. Patient should arrive early again for the visit on the next day.
- The next day when the patient returns to the clinic (within 23:30-24 hours of the beginning of the test), prompt the monitor to take a Conclusion of Test reading. If an invalid reading occurs for the Conclusion of Test reading, continue to trigger a manual reading until a valid reading is registered. The device will then be removed and the time of the Conclusion of Test will be recorded.
- If ABPM was successful, procedures for Visit 7.2 can be conducted on the same day after the ABPM device is removed and trough seated blood pressure measurement is taken. If done on the same day, procedures for Visit 7.2 should be done prior to administering study medication.
- If the first ABPM attempt was unsuccessful (failed QC), a repeat reading should be taken within 2 days. Patient having two technically unsuccessful ABPM sessions may continue with Visit 7.2. Procedures for Visit 7.2 can be conducted on the same day after the ABPM device is removed and trough seated blood pressure measurement is taken.
- Allow the patient to rest for at least 15 minutes after the monitor is removed. Then take a seated blood pressure measurement. Record the time of this measurement. This should be done prior to administering study medication.
- Administer dose of study medication.
- For further instructions for ABPM measurements, please see [Section 5.1.2](#).
- Instruct patients NOT to take study medication on the morning of the next trial visit.

Visit 7.2 (end of treatment)

- BP measurement and orthostatic blood pressure test should always be done before taking any blood samples.

Proprietary confidential information.

© 2016 Boehringer Ingelheim International GmbH or one or more of its affiliated companies. All rights reserved.

This document may not - in full or in part - be passed on, reproduced, published or otherwise used without prior written permission.

- Collection of urine and blood for laboratory testing.
- PK trough sample should be collected.
- Collect returned medication.
- Patients should be reminded about the importance of following the agreed diet and exercise plan.
- Provide HBGM equipment/supplies and instruct patient on the correct use of HBGM.
- Instruct patient to perform a HBGM test at least once daily during the follow up period. Instruct patient to immediately perform a blood glucose test if they experience signs/symptoms of hypo- or hyperglycemia. Instruct patient to contact site immediately if blood glucose reaches limit described in [Section 4.2.1](#).
- Visit 7.2 is the last visit of the treatment period after ABPM is done. No study medication is administered at this visit.
- Instruct patient to continue to take the current therapy as usual. Additional antidiabetic medication can be started after the follow-up visit, in case there is no medical need for rescue medication before that.

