B Patients will undergo 24-hour ABPM testing. If patients fail the test, this procedure should be repeated. Each patient will be allowed a maximum of two attempts within the visit window to obtain one successful measurement starting at each of the ABPM time points (Visit 2.2, 5.1 and 7.1). If the ABPM testing is successful, procedures for the subsequent visit can be conducted on the same day after the ABPM device is removed and trough seated blood pressure measurement is taken.

Visit 2.2 ABPM and any repeat measurements if required should be performed during the run-in period within 7 days prior to Visit 3 (Day 1). Day 1 is the day of randomisation, not the day ABPM is applied.

Visit 5.1 ABPM and any repeat measurements if required should be performed within 7 days prior to Visit 5.2 (Day 85).

Visit 7.1 ABPM and any repeat measurements if required should be performed within 7 days prior to Visit 7.2 (Day 169). dx

C Diligent diet and exercise counselling by a diet specialist or trained staff member at visit 2.1. Counselling is based on local diet recommendations and should include a food log (recording of food intake for 3 consecutive days in the week before the actual visit). At all visits, patients should be reminded about the importance to follow the recommended diet and exercise plan.

D In addition to the visit indicated, ECG should be recorded in case of respective cardiac symptoms (indicating rhythm disorders or cardiac ischemia).

Proprietary confidential information.

© 2016 Boehringer Ingelheim International GmbH or one or more of its affiliated companies. All rights reserved.

This document may not - in full or in part - be passed on, reproduced, published or otherwise used without prior written permission.

- E For female patients (local urine pregnancy test in women of child-bearing potential).
- F Fasting blood and urine samples to be collected, for central labs at each visit indicated (refer to Lab manual). A urine dipstick to be done locally; upon positive result at site for leukocyte esterase (WBC) or nitrites a midstream urine sample should be taken and sent for urine culture analysis (central lab).
- G For the screening Visit 1, laboratory tests only include liver transaminases, alkaline phosphatase, serum creatinine, TSH and urinalysis. Patients do not have to be fasting.
- H Only screening relevant demographics (gender, date of birth).

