- I The ABPM **device** is attached on the mornings of Visit 2.2, 5.1 and 7.1 before medication intake for measuring ABPM. This also applies to visits for repeat ABPM testing if required. Patients must have a successful completion of V2.2 ABPM prior to randomisation. Do NOT contact IRT system or dispense randomised study drug until after a successful 24-hour ABPM is complete. If after two attempts a successful reading is not achieved at either Visit 5.1 or Visit 7.1, patients should continue with the next scheduled visit (Visit 5.2/Day 85 or Visit 7.2/Day 169 respectively).
In case the ABPM must be repeated, the patient should continue taking trial medication. If possible, ABPM should take place within the visit window in the [Flowchart](#). If two doses of study medication are taken when the monitor is attached, then the ABPM should be repeated.

At the conclusion of each attempt, patient should be allowed to rest for at least 15 minutes after removal of the ABPM and a trough seated blood pressure measurement should be taken prior to intake of study medication.

- L Instruction and handover of device at Visit 2.1. Daily measurements during Run-in and Follow-up should be performed. During the treatment period, a weekly test is recommended. During the whole trial participation, additional measurements should be done in case of hypo- or hyperglycemia related symptoms.
- M At all visits the respective kit number has to be allocated to the patient via an interactive response technologies (IRT) system. All visit activities must be completed before contacting IRT.
- N At Visit 4 all patients will be dose escalated through an IRT system.
- O Visit 6 will be conducted as a phone visit.

- Q All visit activities must be completed and continued eligibility for randomisation or dosing confirmed prior to using IRT.
- R At Visit 2.1 the food log is dispensed only and to be completed for three consecutive days prior to Visit 3.

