4.2.1 Rescue medication, emergency procedures, and additional treatments

Throughout the duration of the trial, patients should continue to take their current therapy, the dose of which should remain unchanged if at all possible (for further details see below). This medication will not be provided as part of the clinical trial supplies, unless required by local laws and regulations.

Rescue medication, for the treatment of hyperglycemia, can be initiated during the double-blind treatment period of the trial (i.e. from Visits 3-7.2) and during follow up period but only if the criteria below are met:

- Week 1 – 12 (i.e. up to and including the result from Visit 5.2):
The patient has a glucose level > 270 mg/dl (> 15.0 mmol/l) after an overnight fast
- Week >12 – 26 (i.e. from the day after Visit 5.2 onwards):
The patient has a glucose level > 200 mg/dl (> 11.1 mmol/l) after an overnight fast

Proprietary confidential information.

© 2016 Boehringer Ingelheim International GmbH or one or more of its affiliated companies. All rights reserved.

This document may not - in full or in part - be passed on, reproduced, published or otherwise used without prior written permission.

The above results should be confirmed, meaning that there is a minimum of two measurements, at least one of which should be performed after an overnight fast at the investigational site, and on a different day to the initial (overnight fast) measurement.

A FPG and an HbA1c sample should be taken before initiation of rescue therapy and sent to central lab for analysis. The HbA1c sample is not required if a sample has been taken and sent to the central lab for analysis within the last 4 weeks.

Special attention must be paid to monitor for instances of DKA. All patients must be made aware of this potential risk and need to be instructed to contact the Investigator or other healthcare professional in case of symptoms of DKA. For further details see [Section 2.3](#).

In case of a suspected DKA the Investigator should ensure that appropriate tests are performed at the earliest opportunity according to local guidelines, such as a blood gas test (i.e. pH, bicarbonate; the results will be collected on the relevant page of the eCRF) and that the patient is appropriately treated (i.e. hospitalized or referred to emergency treatment) according to local treatment guidelines.

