Proprietary confidential information.

© 2016 Boehringer Ingelheim International GmbH or one or more of its affiliated companies. All rights reserved.

This document may not - in full or in part - be passed on, reproduced, published or otherwise used without prior written permission.

Renal function impairment will be classified in the following way:

- eGFR \geq 120 ml/min/1.73m²;
- eGFR 120-60 ml/min/1.73m²;
- eGFR \leq 60 ml/min/1.73m²

These 3 classes of renal impairment will be the basis for stratification at randomisation

Empagliflozin influences hepatic glucose output and hepatic triglyceride mobilization which could theoretically reduce fat stores in the liver. This may improve liver function and reduce the burden of NAFLD. NAFLD fibrosis score will be used to assess changes in the status of NAFLD.

NAFLD fibrosis score will be calculated in-house:

$$\text{NAFLD Fibrosis Score} = -1.675 + 0.037 \times \text{age (yr)} + 0.094 \times \text{BMI (kg/m}^2\text{)} + 1.13 \times \text{IFG/diabetes mellitus (yes = 1, no = 0)} + 0.99 \times \text{AST/ALT ratio} - 0.013 \times \text{platelet (x10}^9\text{/L)} - 0.66 \times \text{albumin (g/dl)}$$

Pregnancy testing (urine) will be performed in female patients of child-bearing potential only according to the time points indicated in the [Flow Chart](#).

Criteria for hypoglycaemic events

Every episode of plasma glucose \leq 70 mg/dl (3.9 mmol/l) should be documented in the eCRF with the respective time and date of occurrence. Any hypoglycemia with glucose values $<$ 54 mg/dl ($<$ 3.0 mmol/l) and all symptomatic and severe hypoglycemias should be documented as an AE "hypoglycaemic event".

For the analysis, all hypoglycemias will be classified according to the following criteria:

- Asymptomatic hypoglycemia: Event not accompanied by typical symptoms of hypoglycemia but with a measured plasma glucose concentration \leq 70 mg/dl (3.9 mmol/l)
- Documented symptomatic hypoglycemia with glucose concentration \geq 54 mg/dl and \leq 70 mg/dl (\geq 3.0 mmol/l and \leq 3.9 mmol/l): Event accompanied by typical symptoms of hypoglycemia
- Documented symptomatic hypoglycemia with glucose concentration $<$ 54 mg/dl ($<$ 3.0 mmol/l): Event accompanied by typical symptoms of hypoglycemia but no need for external assistance
- Severe hypoglycaemic episode: Event requiring the assistance of another person to actively administer carbohydrate, glucagon or other resuscitative actions.

Proprietary confidential information.

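### No check of the home glucose log is scheduled between Visit 5.2 and Visit 7.2, so asymptomatic low values, and high values the patient does not phone in, can reach the site up to 12 weeks late

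*Protocol*

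**What the plan says.** - **Visit schedule.** Protocol Section 6.2 makes the Flow Chart the list of procedures per visit. Its HBGM row is marked at Visits 2.1, 3, 4, 5.2, 7.2, PTD and 8, and is blank at Visits 6 and 7.1. AEs are marked at Visits 6 and 7.1, and concomitant therapy at Visit 6. Footnote O reads "Visit 6 will be conducted as a phone visit".
- **Visit 6 detail.** Section 6.2.2 adds two reminders: "Remind the patient to arrive half an hour earlier for the next scheduled visit (Visit 7.1"), and not to take study medication on that morning.
- **Log review.** Section 5.2.5 says review is required, without naming visits. Patients who forget the log are covered by "they should be reminded to record HBGM values on the Log and return it at the next visit".
- **Low values.** Under Section 5.2.3, every episode at or below 70 mg/dl "should be documented in the eCRF with the respective time and date of occurrence". Any hypoglycaemia below 54 mg/dl is also an AE, with or without symptoms.
- **High values.** Section 4.2.1 lowers the fasting rescue limit from above 270 mg/dl to above 200 mg/dl "from the day after Visit 5.2 onwards".
- **Calls from the patient.** At Visit 5.2 patients are told to contact the site if glucose reaches the Section 4.2.1 limit. In Section 5.2.5 the instruction to call below 54 mg/dl stands in the run-in and follow-up paragraph. The paragraph on the randomised period does not repeat it.

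**The concern.** The protocol relies on home monitoring as one of its safety measures (Section 2.3) and asks for one fasting test a week during treatment. In the second half of treatment, no scheduled contact has the site look at those readings.

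Two kinds of reading are affected, and they are separate matters:

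- **Asymptomatic low values.** The patient has no symptom to report when asked about AEs. The only numeric glucose limits in Section 4.2.1 are for high values, so the treatment-period call instruction does not clearly cover low ones. Patients on a sulfonylurea are eligible, and Section 2.3 notes slightly more hypoglycaemia on empagliflozin with that background.
- **High values above the lowered rescue limit.** These depend on the patient recognising the limit and calling. Section 6.2.2 lists no blood draw at Visit 6 or Visit 7.1 that would show them otherwise.

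At stake is the timeliness of safety monitoring. Hypoglycaemic events are a protocol safety endpoint, and SAP Section 7.8.1.4 counts an asymptomatic value below 54 mg/dl as a hypoglycaemic AE.

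**Working it through.** **Inputs (Flow Chart).** Visit 5.2 is Day 85 (window -7/+7), Visit 6 is Day 127 (±7), Visit 7.1 is Day 162, and Visit 7.2 is Day 169 (+7). Footnote B confirms the Visit 5.2 day: "Visit 5.1 ABPM and any repeat measurements if required should be performed within 7 days prior to Visit 5.2 (Day 85"). As (day - 1)/7, Days 85, 127, 162 and 169 are weeks 12, 18, 23 and 24, matching the Flow Chart's week labels.

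**Interval as planned.**
- Visit 5.2 to Visit 7.2: 169 - 85 = 84 days; 84/7 = 12 weeks, or about 12 weekly readings. This is half of the 24-week treatment period.
- Window extremes: Visit 5.2 seven days early is Day 78 and Visit 7.2 seven days late is Day 176; 176 - 78 = 98 days.

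**Site contacts inside the interval.**

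| Contact | Days after Visit 5.2 | AEs | Concomitant therapy | HBGM |
|---|---|---|---|---|
| Visit 6 (phone) | 127 - 85 = 42 | yes | yes | no |
| Visit 7.1 (clinic) | 162 - 85 = 77 | yes | no | no |

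**Interval if the log is read out at Visit 6.**
- Planned: 127 - 85 = 42 and 169 - 127 = 42 days, so the longest is 42 days, or about 6 weekly readings.
- Window extremes: Visit 6 falls between Days 120 and 134; 134 - 78 = 56 and 176 - 120 = 56, so the longest is 56 days.

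**Route to the site, by type of event.**

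| Event after Visit 5.2 | Route before Visit 7.2 |
|---|---|
| Symptomatic or severe hypoglycaemia | AE collection at Visits 6 and 7.1 |
| New or changed medication | Concomitant therapy check at Visit 6 |
| High value at the rescue limit | Patient's call only |
| Asymptomatic value below 54 mg/dl | None scheduled; call instruction not repeated for the treatment period |
| Asymptomatic value of 54 to 70 mg/dl | None scheduled |

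**The case against.** **The HBGM row may not be a review schedule.** Footnote L covers handover of the device and test frequency. The matching bullets in Section 6.2.2 speak of supplies and instruction, and none mentions log review even at marked visits. Supplies cannot be handed over by phone, so a blank at Visit 6 is natural. This stands as far as it goes: a blank cell does not prove that no site would look at the log. But if the row does not schedule the review, the protocol names no visit for a review that it requires. Either reading leaves something to reconcile.

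**The patient's call is not the only route.** This stands. The Visit 6 bullets are supplementary detail, and the Flow Chart puts AE and concomitant therapy checks on that call. A reader might infer that nothing reaches the site unless the patient calls; for symptomatic or severe events and new medication that is wrong.

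**Nothing is shown to be lost.** This stands too. The log is a source document, its review is required, HBGM is marked at Visit 7.2, and a forgotten log is to come back at the next visit. Section 5.2.2.2 collects AEs to the end of the patient's trial, so a low value found at Visit 7.2 can still be recorded with its date. Loss would need an unrecorded value or an unreturned log.

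**The primary endpoint is not shown to be affected.** A reader might infer that unseen high readings shift which HbA1c values are censored. SAP Section 6.6.1 ties censoring to actual use or dose change of antidiabetic medication for at least 7 consecutive days, not to log readings. Section 4.2.1 requires confirmation at the site and leaves rescue to the investigator. No HbA1c is scheduled between Visits 5.2 and 7.2, so the exact rescue date within that gap does not change which scheduled value is set to missing.

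**No passage sets a maximum review interval.** True. The case for a mid-interval check rests on its low cost and on the protocol's own documentation and AE requirements, not on a breached limit.

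**Conclusion.** The point holds as one of timeliness. Followed as written, the plan lets asymptomatic low values, and high values the patient does not phone in, go unseen by the site for up to 84 days (98 at the window extremes). That interval begins when the fasting rescue limit is lowered. It is a cheap improvement to safety monitoring, not a threat to the primary analysis.

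The conclusion assumes that sites review the log only where the Flow Chart marks HBGM, and that a patient without symptoms does not volunteer a low reading during AE questioning. Neither can be settled from the documents. They also give no rate of asymptomatic readings below 54 mg/dl on a weekly fasting test, so the number of patients affected is not estimated. Section 2.3 describes the hypoglycaemia risk as low.

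The documents do not support saying that readings are lost, that the patient's call is the only route, or that HbA1c censoring changes.

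**What to change.** 1. Reconcile the Flow Chart HBGM row, the Visit 6 list in Section 6.2.2 and Section 5.2.5, so that the visits at which the log is reviewed are named.
2. Include Visit 6 among them: on the existing call the patient reads out the entries since Visit 5.2, and the site applies Sections 5.2.3 and 4.2.1 as already written.
3. State whether the Section 5.2.5 instruction to call below 54 mg/dl applies during the treatment period. The sponsor must settle this; no answer is proposed here.

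The planned interval between checks falls from 84 to 42 days, and from 98 to 56 at the window extremes. No glucose limit, dose or rescue rule changes, and no visit is added. The cost is an amendment line and a few minutes per call. The drawback is that values read out by phone can be verified against the written log only at a later clinic visit.
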